10.7.2 Vital Signs

Vital signs (systolic and diastolic blood pressure) and their changes from baseline (pre-dose on Day 1) on Week 4 and Week 8 will be summarized by treatment using descriptive statistics and the 95% CI of the mean.

10.7.3 ECGs

10.7.3.1 12-Lead ECGs

ECG parameters (HR, QTcF, QRS, and PR) will be summarized on Day 1 and Week 8 by treatment using descriptive statistics and the 95% CI of the mean. The nominal recorded value will be used in the calculation. In addition, their changes from baseline will be summarized using descriptive statistics and 90% CI.

In addition, the number and percentage of subjects with prolonged QTcF will be summarized using counts and percentages on Day 1, and Week 8 using the following thresholds:

- QTcF >450 ms for males and >470 ms for females
- QTcF >480 ms for males only
- QTcF >500 ms
- Change from baseline in QTcF >30 ms
- Change from baseline in QTcF >60 ms

12-lead ECG numerical parameters (HR, QTcF, PR and QRS) will not be included in the statistical analysis in the following cases:

- patients with a pacemaker already in place at study entry, identified by the presence of at least one of the following Preferred Terms in the medical/surgical history or concomitant diseases: “Cardiac pacemaker battery replacement”, “Cardiac pacemaker evaluation”, “Cardiac pacemaker insertion”, “Cardiac pacemaker replacement”, “Electrocardiogram pacemaker spike”, “Pacemaker generated arrhythmia”, “Pacemaker generated rhythm”, “Pacemaker syndrome”, “Cardiac assistance device user”;
- patients with a pacemaker implanted during the study, identified by a procedure coded with the Preferred Term “Cardiac pacemaker insertion” (other relevant cases may be identified in the Data Review Report). In this case, only the parameters assessed in a date \geq start date of the procedure will be excluded from the statistical analysis;
- patients with atrial fibrillation as concomitant disease, identified by the presence of at least one of the following Preferred Term: “Atrial fibrillation”, “Cardiac fibrillation”;
- ECGs with PR=0, since this is indicative of poor quality or inevaluable ECG result. Note that this does not apply to all ECGs for the patient, but only the ECGs with PR=0.

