7.2.4 Physical Exam and assessment of oral candidiasis

A full physical examination will be performed at V1-V4 and Early Termination, including an assessment of oral candidiasis.

Oropharyngeal candidiasis is a condition commonly associated with the use of ICS, and is caused by the Candida fungus. This side effect may be attributed to the topical effects of these medications on the oral mucosa.[\[21\]](#) Generalized immunosuppressive and anti-inflammatory effects of steroids are thought to play a major role in the pathogenesis of candidiasis.[\[65\]](#) Asthmatics who are using β -2

agonists show a decreased salivary flow rate, which in turn can be associated with higher oral Candida counts.[\[66\]](#)

The subject's mouth and throat will be visually inspected by the investigator at every study visit to look for the presence of characteristic-looking white lesions / oral thrush. If deemed necessary by the investigator to confirm the diagnosis, the suspected lesion should be swabbed/scraped with a sterile cotton and the tissue sample sent to a laboratory for microscopic and culture identification.

Appropriate treatment of oropharyngeal thrush (e.g. using topical rinses and oral anti-fungal agents) can be prescribed at the discretion of the study investigator as deemed necessary throughout the study.

7.2.5 12-lead ECG

A local ECG instrument will be used. A single ten-second 12-lead ECG will be performed before spirometry, bronchodilator, administration of run-in ICS (V1) and study drug (V2, V4) to verify the subject's cardiac safety parameters and his/her eligibility. Prior to recording, the subject should be at rest for at least 5 minutes.

Safety ECGs will be taken using the site's own instrument. Standard electrode placement will be used for these ECG, including placing the limb leads, dual snap electrodes will be used for the precordial leads. ECG will be evaluated by the investigator/sub-investigator on-site for any abnormality and clinical significance.

QTc value will be calculated using the Fridericia formula (Fridericia-corrected $QTc = \frac{QT}{\sqrt[3]{RR}}$). It will be calculated automatically by the ECG recorder. Heart rate (HR), PR and QRS values will be also evaluated from ECGs at all visits.

ECGs with computerized protocol interpretation are considered normal if

- 40 bpm \leq Heart rate \leq 110 bpm,
- 120 ms \leq PR \leq 210 ms,
- QRS \leq 120 ms.

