9. SAFETY ASSESSMENTS

- Adverse Events (AEs), Adverse Drug Reactions (ADRs)
- Vital signs (systolic and diastolic blood pressure)
- 12-lead ECG parameters (HR, QTcF, QRS, PR)
- Standard blood chemistry and hematology
- 24-h Urinary Free Cortisol and Creatinine

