12.3.6 Safety variables

Adverse Events

All adverse events starting on or after the time of first study drug intake will be classified as Treatment Emergent Adverse Events (TEAEs). Any adverse event started after the informed consent signature and before the time of first study drug intake will be classified as pre-treatment adverse event. Pre-treatment adverse events will be listed only.

The number of TEAEs and the number and percentage of subjects who experienced at least one TEAE will be presented by treatment for all AEs, ADRs, serious AEs, serious ADRs, severe AEs, AEs leading to study discontinuation and AEs leading to death. Summaries will be presented overall and by system organ class and preferred term based on the MedDRA dictionary.

Vital signs

Vital signs (systolic and diastolic blood pressure) and their changes from baseline (Visit 2) will be summarized by treatment using descriptive statistics and the 95% CI of the mean.

ECG

12-lead ECG parameters (HR, QTcF, QRS and PR) and their changes from baseline (Visit 2) will be summarized by treatment using descriptive statistics and the CI of the mean (95% CI for absolute values and 90% CI for the changes from baseline).

The number and the percentage of subjects with a:

- QTcF >450ms (males only), >470ms (females only), >480ms (males only) and >500ms
- change from baseline (Visit 2) in QTcF >30ms and >60ms
- at post-baseline visit will be presented by treatment group.

Laboratory parameters

Shift tables from screening to the end of treatment, based on normal ranges, will be presented by treatment group for the laboratory parameters.

Mean change from baseline (Visit 2) to the end of treatment in 24-h urinary free cortisol and creatinine will be calculated with its 95% CI by treatment group.

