8.1 General Methods

Hypothesis testing will be carried out at the $\alpha = 0.05$ level (two-sided). Statistical significance will be declared if the p-value is less than 0.05, with p-values for the primary efficacy analysis adjusted for multiplicity as described in Section 8.2.

For **continuous variables**, summary statistics will include the number of non-missing observations, mean, standard deviation, 95% (or otherwise) confidence interval of the mean (only in the efficacy and safety analyses, unless otherwise specified), minimum, median and maximum.

For **qualitative variables**, the number (n) and percentage (%) of subjects with non-missing data per category will be the default summary presentation, and where appropriate and present, the number of missing values as a “Missing” category. Unless otherwise specified, the denominator for each percentage will be the number of non-missing observations within the analysis set and treatment group.

General rules to be used for reporting the number of decimal places for derived variables in the listings (in the analyses rounding will not be performed):

- BMI, treatment exposure (days): whole numbers;
- Time to discontinuation (weeks), duration of smoking (years), time since first asthma diagnosis (years), compliance, average use of rescue medication (number of puffs/day), percentage of rescue medication-free days, asthma symptoms scores, percentage of asthma symptoms-free days, percentage of asthma control days: 1 decimal place;
- Change from baseline/pre-dose: same as the variable considered.

The following rules on decimal places will be considered for the results of the analyses (if the analyses are performed on derived variables, the level of precision of the actual data is derived from the previous list):

- min, max: same as actual data;
- mean and its confidence limits (unadjusted and adjusted), adjusted difference between means and its confidence limits, SD, median: actual data + 1 decimal place;
- percentage: 1 decimal place;
- P-values: 3 decimal places; if the p-value is less than 0.001, it will be presented as <0.001.

In general, additional to the analysis model results presented in TLFs, the full SAS output generated for all the analyses will be presented to the sponsor as a standalone document. SAS output results will be delivered only after DB lock.

Calculation of adjusted means (least squares means):

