10.8 Early Termination and Unscheduled Visits

The handling of the early termination efficacy and safety assessments in the statistical analyses will be discussed during the Data Review Meeting and the decisions will be fully documented in the Data Review Report.

With regards to unscheduled assessments, will be evaluated case by case during the Data Review Meeting.

The following rules on data re-allocation will be considered:

- Data collected at multiple visits (spirometry, ACQ score, vital signs, laboratory data, and ECG) recorded at the study termination visit for discontinued patients will be re-allocated by selecting the next visit at which the assessment was planned. For each assessment, only the visits at which the assessment was scheduled will be considered for re-allocation. This means that ECG and laboratory data can be re-allocated only to Visit 4. For example, if the last visit performed before the study termination visit was Visit 2, the data recorded at the study termination visit will be re-allocated to Visit 3 for spirometry, ACQ score, and vital signs, and to Visit 4 for 12-lead ECG and laboratory data. If the study termination visit was performed less than 7 days after the preceding visit, then the data recorded at the study termination visit will not be re-allocated and they will be excluded from the statistical analysis.
- For discontinued patients, efficacy data recorded in the diaries from the last visit performed before the study termination visit or the date of discontinuation onwards will be reallocated to the next expected inter-visit period;
- in case of missing intermediate visit not due to the re-allocation of data collected at the study termination visit (e.g., Visit 3 missing, but Visits 2 and 4 performed), an expected date for the missing Visit 3 will be imputed in order to define the inter-visit periods for diary data. The expected date for the missing Visit 3 will be imputed as follows: Visit 3 expected date = Visit 2 date + 28 days.
- Additional unscheduled/optional assessments will be considered on a case-by-case basis and their inclusion in the analysis will be discussed at the DRM and confirmed in the DRR prior to data base lock and unblinding.

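### The planned ECG outlier counts can leave out some early-termination and unscheduled tracings; counting any ECG after first study drug intake would close the gap

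*SAP*

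**What the plan says.** - **Safety variables.** Protocol 9 lists "12-lead ECG parameters (HR, QTcF, QRS, PR") among the safety assessments.
- **Schedule.** Protocol 7.1, Table 1 and its footnotes place ECGs at Visits 1, 2 and 4 and at early termination. Visit 3 has none.
- **Outlier counts.** Protocol 12.3.6 plans counts for QTcF thresholds only, which "at post-baseline visit will be presented by treatment group". SAP 10.7.3.1 plans the same thresholds: "In addition, the number and percentage of subjects with prolonged QTcF will be summarized using counts and percentages on Day 1, and Week 8".
- **Continuous summaries.** SAP 10.7.3.1 adds: "ECG parameters (HR, QTcF, QRS, and PR) will be summarized on Day 1 and Week 8 by treatment using descriptive statistics". SAP 8.1 defines these summaries to include "minimum, median and maximum".
- **Early termination.** SAP 10.8 re-allocates the ECG from a termination visit to Visit 4. If that visit came less than 7 days after the one before it, the data are not re-allocated and are left out of the analysis.
- **Unscheduled tracings.** SAP 10.8: "Additional unscheduled/optional assessments will be considered on a case-by-case basis and their inclusion in the analysis will be discussed at the DRM". The sentence goes on to require confirmation before database lock and unblinding.
- **Adverse events.** Protocol 7.2.5 and 10.8 make ECG changes that the investigator considers clinically significant reportable as adverse events. SAP 10.7.1 tabulates treatment-emergent events by arm.
- **Normal limits.** Protocol 7.2.5 gives ranges under the words "ECGs with computerized protocol interpretation are considered normal if": HR 40 to 110 bpm, PR 120 to 210 ms, QRS up to 120 ms. No planned table uses them.

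**The concern.** An outlier table exists to show how many subjects in each arm had a marked individual value, which means can hide. It should therefore draw on every tracing recorded after dosing began. Here one fixed rule discards some on-treatment tracings, and another group enters only by judgement on each case. The subjects affected are those who stopped early and those who had an ECG outside the schedule. A safety count should not depend on the date of a termination visit relative to a visit with no ECG, or on a decision made when the result can be seen.

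**Working it through.** No sample size, power or alpha figure bears on this point, so there is no plan figure to reproduce. The check sets the rules side by side and then sizes the gap.

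**1. Tracings available.** A completer has one scheduled post-baseline ECG, at Visit 4. A subject who stops early has one, at the termination visit, if that visit takes place.

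**2. What the Day 1 column adds.** SAP 7.2.11 takes the pre-dose Day 1 ECG as baseline, so change from baseline on Day 1 is zero by definition. Exclusion criterion 13 bars QTcF above 450 ms (males) or 470 ms (females) at randomization. Apart from eligibility deviations, only the Week 8 column can hold outliers.

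**3. The 7-day rule applied to ECGs.** Visit 3 is taken at 28 days after Visit 2.

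| Termination visit | Days since treatment start | Days since preceding visit | ECG under SAP 10.8 |
|---|---|---|---|
| 6 days after Visit 2 | 6 | 6 | excluded |
| 7 days after Visit 2 | 7 | 7 | counted at Visit 4 |
| 6 days after Visit 3 | 28 + 6 = 34 | 6 | excluded |
| 7 days after Visit 3 | 28 + 7 = 35 | 7 | counted at Visit 4 |

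With the ±2-day window at Visit 3, the 34 days become 32 to 36. A tracing after 7 days of treatment is counted at Week 8, while one after about 34 days is dropped. In the dropped case no other post-baseline ECG was scheduled.

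**4. Unscheduled ECGs.** SAP 10.8 gives no default, either in or out. Decisions precede unblinding, but nothing in the SAP hides the value from those deciding.

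**5. What the adverse event route catches.** It catches what the investigator calls clinically significant. Take an assumed QTcF of 400 ms at baseline and 435 ms on treatment. The change is 435 − 400 = 35 ms, which meets the SAP's >30 ms threshold, yet 435 ms lies below both sex-specific limits. An investigator could reasonably not report it. If the tracing is excluded under step 3 or not admitted under step 4, that subject is in neither the outlier counts nor the adverse event tables.

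**6. Size.** With 117 randomized per arm, one uncounted subject is 1/117 = 0.9%. The documents do not give the number of early terminations or their timing. As an assumed ceiling, let all planned non-evaluable subjects stop early: 117 − 99 = 18 per arm. If stopping is spread evenly over 56 days, the two 7-day windows cover 14/56 = 25%, or 18 × 0.25 = 4.5 subjects per arm. The range is 0 (none stop in a window) to 18 (all do). These are tracings at risk of exclusion, not outliers.

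**7. HR, PR and QRS (optional part).** The shift in an arm mean from k subjects each changing by s is k × s / n. Three of 117 subjects (2.6%) with an assumed PR rise of 40 ms move the mean by 3 × 40 / 117 = 1.03 ms. Over 1 to 5 subjects and 20 to 60 ms, the shift runs from 1 × 20 / 117 = 0.17 ms to 5 × 60 / 117 = 2.56 ms. The mean would not reveal this. The maximum would show the largest value, but not how many subjects crossed a limit.

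**The case against.** The case for leaving the plan alone has real weight.

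- Most early-termination ECGs do reach the Week 8 counts through re-allocation.
- Unscheduled ECGs are not excluded by default, and the decision comes before unblinding.
- SAP 10.8 lets the blind review revisit its own rules, and the preceding visit could be read as the preceding visit with an ECG.
- Clinically significant changes reach the adverse event tables, and all ECG results are listed by subject.
- Counting any ECG gives subjects with extra tracings more chances to be counted.

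All of this stands, and it keeps the point small. It does not remove it: the exclusion is written without the narrower reading, a listing gives no comparison by arm, and the adverse event route depends on each investigator's opinion.

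A reader might infer more than the documents support:

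- **That HR, PR and QRS extremes are missing from every table.** They are not. For scheduled ECGs, minimum and maximum appear in Table 14.3.5.1.
- **That the SAP departs from the protocol by counting only QTcF.** Protocol 12.3.6 does the same. The ranges in protocol 7.2.5 describe a normal computerized reading and are not stated as analysis thresholds.
- **That heart-rate counts are needed because rescue albuterol use may differ by arm.** Albuterol is to be withheld for 6 hours before scheduled visits and the visit rescheduled if it was used, so the Week 8 tracing is designed to avoid recent use.

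**Conclusion.** The gap is real and narrow. The QTcF outlier counts can omit an on-treatment tracing in two situations: a termination visit less than 7 days after the preceding visit, and an unscheduled ECG not admitted at the data review. If the finding is also not judged clinically significant, the subject appears in neither the outlier counts nor the adverse event tables. Each such case is 0.9% of an arm, and the number of cases cannot be known from the documents. The conclusion rests on reading the 7-day rule as written and on the absence of an ECG at Visit 3. It does not touch the primary analysis. This is a low-cost improvement to a safety table. The absence of HR, PR and QRS counts is a matter of preference, not an error.

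**What to change.** In SAP 10.7.3.1, define the ECG outlier counts as the number and percentage of subjects, by arm, with at least one qualifying value on any ECG after first study drug intake. State that this covers Week 8, every early-termination visit (including those less than 7 days after the preceding visit) and unscheduled tracings. Use as denominator the Safety population subjects with at least one such ECG, and for the change thresholds also a baseline ECG. Keep the exclusions already listed there for pacemakers, atrial fibrillation and PR = 0. Keep the by-visit means on scheduled or re-allocated ECGs, and note in SAP 10.8 that the 7-day exclusion and the case-by-case rule do not apply to these counts.

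Optional: add counts by arm of post-baseline HR, PR and QRS outside the protocol 7.2.5 limits. This goes beyond protocol 12.3.6 and does not correct a departure from it.

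Cost: a short change of SAP wording and reprogramming of the prolonged-QTcF tables on data already collected, plus one table if the option is taken. The downside is that subjects with extra ECGs have more chances to be counted. A footnote giving the number of unscheduled ECGs per arm would let a reader judge this.

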10.7.4 Clinical Laboratory Evaluation

Shift tables will be presented for hematology and biochemistry parameters by treatment group at Day 1 and Week 8.

The categories for the shift tables are as follows:

- Low clinically significant
- Low not clinically significant
- Normal
- High clinically significant
- High not clinically significant

In addition, all laboratory data will be listed, with abnormal values flagged. Mean change from baseline (Visit 2) to the end of treatment in 24-h urinary free cortisol and creatinine will be calculated with its 95% CI by treatment group.

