	
year, vital signs and training for the use of inhalers). Concomitant Medications and Adverse Events will be assessed. Dispensing of subject diary will be done. Eligible subjects will be provided with a container for the 24-h urine collection, to be returned to the site the day after completing the collection, 1-2 days before or on the date of their next visit (V2). This visit will be followed by a 14±2 day run-in period. Treatments that are disallowed by the protocol are to be discontinued at Visit 1, including current ICS (as monotherapy or as combination ICS/LABA). The subjects will be instead prescribed an equivalent daily dose of ICS as beclomethasone dipropionate (QVAR® 40 or 80µg/actuation) and this treatment regimen should remain stable for the entire run-in period. Subjects will receive rescue medication (albuterol) with instructions for “on demand” use for the entire study period.
 
▪ At randomization visit (Visit 2), inclusion/exclusion criteria, adverse events and concomitant medications will be reviewed. Eligibility recheck will be completed. Pre-dose vital signs and spirometry testing [FEV₁, FVC] will be performed. A 12-lead ECG, physical examination, urine pregnancy test will be performed, and training on the use of inhalers will be conducted. The ACQ will be assessed. The 24-h urine collection container will be collected from the subject if not already done, and shipped to a central laboratory for 24-h urine free cortisol and creatinine measurement. Eligible subjects will then be randomized to one of the treatment groups and will receive the 1st dose of study drug under medical supervision. The subjects will then leave the clinical center and will be instructed to return in 4 weeks.▪ At Week 4 (Visit 3) subjects will undergo a physical examination, urine pregnancy test, concomitant medications review, adverse events, study drug dispensation and vital signs assessment. Study drug will be returned and accountability will be performed. Pre-dose spirometry testing (FEV₁, FVC) will be performed and ACQ will be assessed. Subjects will be provided with a container for the 24-h urine collection, to be returned to the site the day after completing the collection, 1-2 days before or on the date of their next visit (V4). The subject will be instructed to return to the clinical center in 4 weeks.▪ At Week 8 (Visit 4) subjects will come to the clinical center and will undergo a physical examination, hematology and blood chemistry, serum/urine pregnancy test and vital signs assessment. A 12-lead ECG will be performed. Concomitant medications and adverse events will be assessed. Pre-dose spirometry testing [FEV₁, FVC] will be performed. No administration of the study drug will take place at V4. The ACQ will be assessed. The 24-h urine collection container will be collected from the subject if not already done, and shipped to a central laboratory for 24-h urine free cortisol and creatinine measurement. Study drug will be returned and accountability will be done. Subject diary will be returned by the subject. After the last assessment a follow-up phone call will be scheduled with the subject.▪ At Week 9 (Visit 5): A safety follow up phone call will be performed by the investigator or designated staff no later than 1 week after the final visit (V4) or Early Termination Visit to check the status of unresolved AEs and to record any new AEs that may have occurred

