7.2.7 Morning Serum Cortisol

On the morning of Visit 1, a blood sample (5mL) will be collected between 7-10 AM to measure basal serum total cortisol level. Serum samples will be analyzed in duplicate in a blinded manner for serum cortisol using solid-phase extraction in combination with liquid chromatography tandem mass spectrometry.[\[70\]](#)

The specific procedures for serum processing and shipping will be provided to the investigator by the laboratory.

7.2.8 24-h Urine Free Cortisol and Creatinine

Cortisol is a steroid hormone synthesized from cholesterol by a multi-enzyme cascade in the adrenal glands. It is the main glucocorticoid in humans. Its production is under hypothalamic-pituitary feedback control. Only a small percentage of circulating cortisol is biologically active (free), with the majority of cortisol inactive (protein bound). As plasma cortisol values increase, free cortisol (ie, unconjugated cortisol or hydrocortisone) increases and is filtered through the kidney's glomerulus. Urinary free cortisol (UFC) correlates well with the concentration of plasma free cortisol. UFC represents excretion of the circulating, biologically active, free cortisol that is responsible for the signs and symptoms of hypercortisolism. UFC is a sensitive test for the various types of adrenocortical dysfunction, particularly hypercortisolism (Cushing syndrome). Subjects with Cushing syndrome due to intake of synthetic glucocorticoids should have suppressed UFC.[\[71\]](#) A measurement of 24-hour UFC excretion, by liquid chromatography-tandem mass spectrometry (LC-MS/MS), is the preferred screening test for Cushing syndrome.[\[72\]](#) LC-MS/MS methodology eliminates analytical interferences including carbamazepine (Tegretol) and synthetic corticosteroids, which can affect immunoassay-based cortisol results.

24-hour urine samples will be collected for the measurement of UFC concentration and creatinine excretion. At V1, eligible subjects will be provided with a container for the 24-h urine collection, to be returned to the site the day after completing the collection, 1-2 days before or on the date of V2. At V3, subjects will be provided with a container for the 24-h urine collection, to be returned to the site after completing the collection, 1-2 days before or on the date of V4. For the purpose of this

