study, a normal range for UFC in subjects ≥ 18 years of age is considered between 4.0 – 50 $\mu\text{g}/24$ hs, and the normal range in adults for 24-h Urine creatinine = 0.63-2.50 g/24hs.[\[73\]](#)

The specific procedures for 24-h urine collection, processing and shipping will be provided to the investigator by the laboratory.

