| WBC: | Leucocytes ($10^9/L$) |

Differential (abbreviation followed by the full name and units)

| | |
|--------|---------------------------------|
| BASO: | Basophil ($10^9/L$) and (%) |
| EOSIN: | Eosinophil ($10^9/L$) and (%) |
| LYMPH: | Lymphocyte ($10^9/L$) and (%) |
| MONO: | Monocyte ($10^9/L$) and (%) |
| NEUT: | Neutrophil ($10^9/L$) and (%) |

Blood Chemistry (abbreviation followed by the full name and units)

| | |
|---------|----------------------------------------|
| ALB: | Albumin (g/L) |
| ALKPH: | Alkaline Phosphatase (U/L) |
| ALT: | ALT (U/L) |
| AST: | AST (U/L) |
| BUN: | Blood Urea Nitrogen (mmol/L) |
| BILDIR: | Direct Bilirubin ($\mu\text{mol}/L$) |
| CA: | Calcium (mmol/L) |
| CHOL: | Cholesterol (mmol/L) |
| CL: | Chloride (mmol/L) |

CREAT: Creatinine ($\mu\text{mol/L}$)
GGT: Gamma-GT (U/L)
GLUC: Fasting Serum Glucose (mmol/L)
K: Potassium (mmol/L)
NA: Sodium (mmol/L)
PROT: Total Protein (g/L)
TRIG: Triglycerides (mmol/L)
URATE: Urate ($\mu\text{mol/L}$)

Results from the central laboratory will include the out of range flag based on the lower and upper limits of normal range. Categories will be

- Low CS
 - Low NCS
 - Normal
 - High NCS
 - High CS, and
 - Missing.
-
- 5: 24-h Urinary Free Cortisol and Creatinine

24-hour urine sample will be collected at Visit 2 and at Visit 4 for the measurement of urinary free cortisol and creatinine excretion.

8 Analysis Methods

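### Home-collected 24-h urinary free cortisol is summarised without creatinine correction or a completeness criterion, so incomplete collection can mimic, mask or dilute adrenal suppression

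*SAP*

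**What the plan says.** - **Analysis.** SAP 10.7.4: "Mean change from baseline (Visit 2) to the end of treatment in 24-h urinary free cortisol and creatinine will be calculated", with a 95% CI by treatment group. Protocol 12.3.6 has the same plan: "in 24-h urinary free cortisol and creatinine will be calculated with its 95% CI by treatment group". The output is Table 14.3.8, which shows urinary free cortisol (UFC) and creatinine as separate variables.
- **Derivation.** SAP 7.2.11 says only: "24-hour urine sample will be collected at Visit 2 and at Visit 4 for the measurement of urinary free cortisol and creatinine excretion". It derives no ratio, checks neither volume nor duration, and does not define a valid sample.
- **Collection.** The subject takes a container home, "to be returned to the site the day after completing the collection, 1-2 days before or on the date of V2" (Protocol 7.2.8), with the same arrangement before Visit 4. The protocol synopsis has the container "shipped to a central laboratory for 24-h urine free cortisol and creatinine measurement", so both analytes come from one collection.
- **Reading of a low value.** Protocol 7.2.8: "Subjects with Cushing syndrome due to intake of synthetic glucocorticoids should have suppressed UFC".
- **Ranges.** Protocol 7.2.8 gives UFC limits of 4.0 to 50 µg/24 h, and "the normal range in adults for 24-h Urine creatinine = 0.63-2.50 g/24hs". Neither range is tied to sample validity. The shift tables (14.3.6 and 14.3.7) cover hematology and biochemistry only. SAP 10.7.4 does have all laboratory data listed with abnormal values flagged, and Listing 16.2.8.3.4 covers the urine results.

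**The concern.** A 24-h excretion in µg is right only if all the urine of the 24 hours is in the container. A missed void lowers the measured cortisol in proportion. Creatinine from the same container falls by the same factor, so it carries the information needed for a correction, but the plan does not use it that way.

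UFC is the only on-treatment cortisol measure with a planned analysis. The protocol schedule takes morning serum cortisol at Visit 1 only. The SAP schedule also ticks Visit 4, but no SAP output reports serum cortisol. In a dose-ranging trial of an inhaled corticosteroid, the description of systemic effect by dose therefore rests on this variable.

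The SAP handles measurement quality elsewhere. It excludes ECGs with PR=0 (10.7.3.1) and repeats the primary analysis on spirometry graded acceptable (8.2). Urine has nothing comparable.

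**Working it through.** The documents give no SD, expected change or power for UFC, so there is no planned figure to reproduce. Only the ranges (UFC 4.0 to 50 µg/24 h, creatinine 0.63 to 2.50 g/24 h) and 117 randomized per arm come from the documents. All other inputs below are assumptions.

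**1. One subject.** Assume true UFC 5.0 µg/24 h, creatinine 1.50 g/24 h, and a quarter of the urine lost.
- UFC: 5.0 × 0.75 = 3.75, below 4.0.
- Creatinine: 1.50 × 0.75 = 1.125 g, still in range.
- Ratio: 5.0/1.50 = 3.75/1.125 = 3.33 µg/g, unchanged.

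With this loss, only true values from 4.0 up to 4.0/0.75 = 5.33 cross the limit.

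**2. Arm mean, no true change.** Let p be the share of subjects under-collecting and L the fraction of urine lost.
- Week 8 only: apparent change = -pL. For p = 5% to 30% and L = 20% to 50%: -1% to -15%.
- Visit 2 only: apparent change = 1/(1 - pL) - 1. Same inputs: +1% to +18%.

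**3. Simulation.** 4,000 arms of 117; mean UFC 20 µg/24 h; UFC CV 50% between and 35% within subjects; creatinine about 1.4 g/24 h with CV 25% and 10%; L = 40%. The ratio was analysed on the log scale.

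| True effect | Under-collecting, Visit 2 / Week 8 | Mean UFC change (µg/24 h) | UFC CI wholly below 0 | Ratio, Week 8 to Visit 2 | Ratio CI wholly below 0 |
|---|---|---|---|---|---|
| none | 5% / 20% | -1.2 | 21% | 1.00 | 2.4% |
| none | 5% / 30% | -2.0 | 46% | 1.00 | 2.2% |
| none | 15% / 15% | 0.0 | 2.5% | 1.00 | 2.4% |
| none | 20% / 5% | +1.2 | 0% | 1.00 | 2.3% |
| 20% fall | none | -4.0 | 99% | 0.80 | 99.8% |
| 20% fall | 15% / 15% | -3.8 | 98% | 0.80 | 99.8% |
| 20% fall | 30% / 5% | -1.9 | 51% | 0.80 | 99.6% |

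The nominal figure with no effect is 2.5%. By hand, the second row is 20 × (1 - 0.30 × 0.40) - 20 × (1 - 0.05 × 0.40) = 17.6 - 19.6 = -2.0. The last row is 16 × 0.98 - 20 × 0.88 = 15.68 - 17.6 = -1.9.

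**4. What the planned creatinine summary would show.** In the first two rows the CI for creatinine change lies wholly below 0 in 79% and 99% of arms. In the 15% / 15% rows it shows nothing.

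**5. The creatinine range as a screen.** A subject with a true output of 1.4 g/24 h can lose 1 - 0.63/1.4 = 55% and still reach 0.63. In the simulation, 86% of Week 8 samples with 40% lost stayed at or above 0.63.

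**6. Precision.** On the log scale, CI width with correction relative to without = sqrt{[ln(1 + CVw²) + ln(1 + 0.10²)] / [ln(1 + CVw²) + ln(1 + CVc²)]}. CVw is within-subject UFC variability, CVc is collection completeness, and creatinine CV is set at 10%.

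| CVc | CVw 30% | CVw 50% |
|---|---|---|
| 5% | 1.04 | 1.02 |
| 10% | 1.00 | 1.00 |
| 20% | 0.88 | 0.94 |
| 25% | 0.81 | 0.91 |

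Correction narrows the CI only when completeness varies more than creatinine does. At a completeness CV of 5% the CI is 2% to 4% wider. The SAP plans an arithmetic mean change, so these ratios are indicative.

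**The case against.** The strongest reply is that the plan already contains the means of detection. Creatinine change stands beside UFC in Table 14.3.8, the central laboratory supplies out-of-range flags (SAP 7.2.11), and the listing shows both analytes by subject. The laboratory's collection procedures (Protocol 7.2.8) or the blind data review (SAP 8.2.1.2) could also deal with poor samples. The variable is descriptive, with no planned test between arms, and anyone can compute the ratio later from the listed data.

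Much of this stands. The creatinine summary would often reveal a large imbalance between visits at group level. It corrects no subject's UFC, however, and it is silent when losses are similar at both visits. A laboratory validity rule cannot be ruled out, but none is in these documents. The SAP's missing-data provision does not clearly reach an incomplete collection, because that still returns a number.

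A reader might infer four stronger things that the documents do not support:
- **That under-collection reads as suppression in general.** This needs worse collection at Week 8 than at Visit 2, and nothing in the documents suggests it.
- **That the comparison across doses is confounded.** Arms are randomized, A to D are double-blind, and nothing suggests that completeness differs by arm. Loss that is similar across arms is noise and dilution.
- **That incomplete collection cannot be told from suppression.** The paired fall in creatinine is evidence, and it is reported.
- **That no output uses the normal ranges for urine.** The listings flag abnormal values. What is missing is a by-arm summary.

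**Conclusion.** The gap is real and modest. Neither document pre-specifies a creatinine correction or a completeness criterion for home-collected UFC, although the means of correction is measured in every container. Incomplete collection can mimic suppression, mask it, or dilute it and add noise, depending on the visit at which it is worse. For a safety variable, masking is at least as serious as a false signal: in the last simulated row a true 20% fall is detected in 51% of arms instead of 99%.

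Every size given rests on assumed shares of under-collection, losses and CVs. The documents supply none of these, and with near-complete collections the effect is negligible. The primary endpoint is not affected. This is a cheap improvement to a descriptive safety analysis and does not invalidate the plan.

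**What to change.** Before unblinding, add to SAP 10.7.4 and Table 14.3.8 the creatinine-corrected UFC (µg cortisol per g creatinine) at Visit 2 and Week 8, and its change from Visit 2 with 95% CI by arm. Keep the uncorrected µg/24 h summary alongside.

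Two limits on related additions:
- A by-arm count of subjects below 4.0 µg/24 h should be read beside the corrected value. On uncorrected UFC alone it would partly count incomplete collections.
- The 0.63 to 2.50 g/24 h creatinine range can serve at most as a crude supportive screen, since it passes most of the incomplete samples simulated above. It should not be the main remedy.

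The cost is a few lines of SAP text and some table rows from data already collected. The downside is that the ratio adds creatinine's own variability and can slightly widen the CI when collections are nearly complete, which is why both values should be shown.
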